6.2 Post-Study Therapy

There are no post-study therapy restrictions.

Confidential Page 42 of 71

7 STUDY PROCEDURES

7.1 Schedule of Evaluations

A schedule of evaluations is provided in the Schedule of Study Events (see Appendix 1).

7.2 Visit Description

7.2.1 Visit 1, Screening (Day -45 to Day -1)

- Preliminary review of inclusion and exclusion criteria
- Obtain signed informed consent for study participation
- Allocation of unique subject number; this number will be used to document the subject data in the case report forms (CRFs) and enrollment log
- Demography date of birth, gender, race
- Medical/surgical history- all relevant prior medical and surgical conditions will be recorded in the CRF. Documented medical conditions will also note the month and year of onset if the condition is still active. The subject's history of NASH treatment will also be collected.
- Concomitant Medications (within 30 prior to screening visit).
- Vital signs (body temperature, heart rate, blood pressure, and respiratory rate after at least 1 minute in a resting position)
- ECG The electrocardiogram (ECG) reading will be assessed for clinical significance by the investigator, and any clinically significant abnormal findings will be noted on the subject's medical history.
- Physical examinations will include an assessment of height, weight and calculation of BMI and an examination of general appearance, skin, eyes, ears, nose, throat, head and neck (including thyroid), lungs, heart, abdomen, musculoskeletal, and nervous system. Any clinically relevant finding is to be documented as a baseline finding. Physical exams that are conducted as standard of care prior to signing informed consent may be used if they are performed within 30 days of injection.
- Blood draw for routine hematology, chemistry, and serum pregnancy test for women of child-bearing potential. Females of child bearing potential are defined as women that are not surgically sterile (hysterectomy, tubal ligation, or bilateral oophorectomy) nor postmenopausal for at least 1 year prior to screening. Women who are not of childbearing potential will not require a pregnancy test.
- Urine collection for routine urinalysis
- Transient elastography will be performed to assess liver fibrosis
- Final confirmatory review of inclusion and exclusion criteria.

AE monitoring will begin from Visit 1 Screening and continue through subject completion of the trial.

Confidential Page 43 of 71

7.2.2 Visit 2 (Day 0) Unfiltered Tc 99m Sulfur Colloid Administration

7.2.2.1 Before Administration of Unfiltered Tc 99m Sulfur Colloid

The following will be completed on the day of administration prior to the administration of unfiltered Tc 99m sulfur colloid:

- A urine pregnancy test for women of child-bearing potential. Females of child bearing potential are defined as women that are not surgically sterile (hysterectomy or bilateral oophorectomy) nor postmenopausal for at least 1 year prior to screening. Women who are not of childbearing potential will not require a pregnancy test.
- Assessment of AEs
- Concomitant medication review
- Vital signs after at least 1 minute in a resting position (body temperature, heart rate, blood pressure, and respiratory rate) within 15 minutes prior to administration of unfiltered Tc 99m sulfur colloid

7.2.2.2 Administration of Unfiltered Tc 99m Sulfur Colloid

IV administration of unfiltered Tc 99m sulfur colloid will be at study time Day 0 Time 00:00. The preferred site of IV placement will be the left or right antecubital vein.

All subjects will receive an on label 8.0 mCi dose of unfiltered Tc 99m sulfur colloid. The filled syringe will be connected to the IV for a slow push injection. At the completion of the injection, a 10 cc sterile normal saline flush will be administered.

The IV administration will be performed in the nuclear medicine department by an onsite Certified Nuclear Medicine Technologist or Nuclear Medicine Physician. Subjects will be continuously monitored for AEs.

7.2.2.3 After Administration of Unfiltered Tc 99m Sulfur Colloid

The following procedures will be completed at the specified times:

- 20 ± 5 Minutes After Administration
 - Assessment of AEs
 - O Vital signs after at least 1 minute in a resting position (body temperature, heart rate, blood pressure, and respiratory rate)
 - o Planar imaging of the liver/spleen followed by SPECT/CT of the liver/spleen and abdomen

Confidential Page 44 of 71

Clinical Study Protocol Number: NAV3-30

7.2.3 Visit 3 (Day 3) Tc 99m Tilmanocept Administration

7.2.3.1 Before Administration of Tc 99m Tilmanocept

The following procedures will be completed on the day of injection prior to the administration of Tc 99m tilmanocept:

- A urine pregnancy test for women of child-bearing potential. Females of child bearing potential are defined as women that are not surgically sterile (hysterectomy or bilateral oophorectomy) nor postmenopausal for at least 1 year prior to screening. Women who are not of childbearing potential will not require a pregnancy test.
- Assessment of AEs
- Concomitant medication review
- Vital signs after at least 1 minute in a resting position (body temperature, heart rate, blood pressure, and respiratory rate) within 15 minutes prior to administration of Tc 99m tilmanocept

7.2.3.2 Administration of Tc 99m Tilmanocept

IV administration of Tc 99m tilmanocept will be at study time Day 3 Time 00:00. The preferred site of IV placement will be the left or right antecubital vein.

All subjects will receive an open label 200 µg dose of Tc 99m tilmanocept at the specified radiolabel dose. The filled syringe will be connected to the IV for a slow push injection. At the completion of the injection, a 10 cc sterile normal saline flush will be administered.

The IV administration will be performed in the nuclear medicine department by an onsite Certified Nuclear Medicine Technologist or Nuclear Medicine Physician. Subjects will be continuously monitored for AEs.

7.2.3.3 After Administration of Tc 99m Tilmanocept

The following procedures will be completed at the specified times:

- 20 ± 5 Minutes After Administration:
 - Assessment of AEs
 - o ECG (completed before vital signs)
 - Vital signs after at least 1 minute in a resting position (body temperature, heart rate, blood pressure, and respiratory rate)
 - o Planar imaging of the liver/spleen followed by SPECT/CT of the liver/spleen and abdomen
- 75 ± 15 Minutes After Administration:
 - Assessment of AEs

Confidential

Clinical Study Protocol Number: NAV3-30

- o Planar imaging of the liver/spleen followed by SPECT/CT of the liver/spleen and abdomen
- 180 ± 15 Minutes After Administration:
 - Assessment of AEs
 - o Planar imaging of the liver/spleen followed by SPECT/CT of the liver/spleen and abdomen
- After Completion of All Imaging:
 - o Blood draw for hematology and chemistry testing
 - o Urine collection for urinalysis

7.2.4 Safety Follow Up Telephone Call (Day 8 ± 3)

A safety follow-up telephone call will be performed 5 ± 3 days after administration of Tc 99m tilmanocept (Day 8 ± 3):

- o Concomitant medication review
- Assessment and review of AEs

Confidential Page 46 of 71

8 PROCEDURES AND VARIABLES

8.1 Population Characteristics

8.1.1 Demographic and Other Baseline Characteristics

Up to six (6) female or male subjects with biopsy-confirmed moderate to severe NASH will be enrolled. Up to six (6) female or male subjects without evidence of any liver or inflammatory diseases will be enrolled. There are no minimum or maximum numbers for gender in the groups.

8.1.2 Medical and Surgical History

Relevant medical and surgical histories will be obtained on all study subjects. For NASH subjects, this will include a history of all NASH treatment.

As part of the medical history, the date of the last spontaneous menstruation will be recorded, if childbearing potential is not excluded by surgical sterilization.

8.1.3 Prior and Concomitant Medication

All prior medications used within the last 30 days before the first screening examination through the 5 ± 3 day post-tilmanocept injection (Day 8 ± 3) follow-up safety telephone call will be documented.

8.2 SPECT/SPECT-CT Image Acquisition

The camera used to obtain the images should be a dual-headed SPECT or SPECT/CT camera equipped with a low-energy, high-resolution collimator with a 15% window (20% can be used if 15% setting not available) centered over a 140keV peak.

The camera must have passed the daily SPECT QC tests as per the manufacturer's recommendation for that day's scan schedule.

Whenever possible, subjects should be asked to void after injection and prior to the first imaging session and again between imaging sessions.

Subjects should be positioned supine with arms at their side. The subject's head, legs, hands, and hips should be in the true anterior position. The subject should be instructed to remain as motionless as possible during the scan, and asked to breathe as shallowly as comfortable when the camera is passing over the chest. To help minimize leg motion, a light taping around the ankles can be used to keep the legs together. A pillow under the knees is often very helpful for comfort.

A planar scan of the liver followed by SPECT/CT should be obtained at the following time points following administration of the specified product:

Unfiltered Tc 99m Sulfur Colloid:

• 20 ± 5 minutes post administration

Tc 99m Tilmanocept:

- 20 ± 5 minutes post administration
- 75 ± 15 minutes post administration
- 180 ± 15 minutes post administration

It is anticipated that the planar scan would be acquired for 25-30 minutes. Using state-of-the-art 2-headed cameras (nominal 20" x 15" FOV), a target of 5-7 million counts should be obtained for the summed view of both heads. For higher activity injections, it may be possible to attain this target in a shorter time, allowing the subject more time off the bed between scans. A simple measure of the subject's "thickness" (i.e. from a lateral visual view, the height of the subject's anterior-most chest/abdomen above the scan bed) should be documented. This will be used for the attenuation correction to be applied to the anterior/posterior views obtained from the planar scan.

Following completion of the planar imaging session at the designated time points, a 3D SPECT/CT should be obtained on the liver, spleen, and abdomen, followed by a patient break.

It is anticipated that each planar or SPECT/CT scan would be acquired for 25-30 minutes (30 minutes preferred). A break between scans should address the comfort of the patient, encouraging the subject to void, consume fluids or food and to move or rest freely. It is very important that the subject remain motionless for the duration of each scan.

The SPECT transverse slices will be reconstructed using the manufacturer's recommended reconstruction algorithms including the recommended attenuation correction.

It is strongly recommended that each site should perform all imaging acquisitions per their camera manufacturer and model parameters and in accordance with their institutional practices for both the planar imaging as well as the SPECT/CT imaging acquisitions.

De-identified DICOM (Digital Imaging Communications in Medicine) copies of all acquired images will be transmitted to Navidea Biopharmaceuticals. The areas of localization will be identified, documented and captured in the CRFs.

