 - Planar imaging of the liver/spleen followed by SPECT/CT of the liver/spleen and abdomen

Visit 3, Day 3:

Pre-Tc 99m Tilmanocept Administration:

- Before administration (Day 3)
 - Urine pregnancy test will be performed for subjects of childbearing potential
 - Assessment of adverse events

Confidential Page 10 of 71

	Concomitant medication review			
	o Vital Signs - within 15 minutes			
	administration	 		
	Tc 99m Tilmanocept Administration: Subjects will receive the open label 200 μg at the specified radiolabeled dose.			
	Post-Tc 99m Tilmanocept	Administration:		
	• 20 ± 5 Minutes Post-Administration:			
	o Assessment o	f adverse events		
	o ECG (comple	eted before vital signs)		
	 Vital Signs 			
		ng of the liver/spleen followed by f the liver/spleen and abdomen		
	• 75 ± 15 Minutes Pos	t-Administration:		
	o Assessment o	f adverse events		
	 Planar imaging of the liver/spleen followed by SPECT/CT of the liver/spleen and abdomen 			
	• 180 ± 15 Minutes Post-Administration:			
	 Assessment of adverse events 			
	 Planar imaging of the liver/spleen followed by SPECT/CT of the liver/spleen and abdomen 			
	After Completion of All Imaging:			
	o Blood draw testing	for hematology and chemistry		
	 Urine collecti 	on for urinalysis		
	Day 8 ± 3 :			
	Safety Follow-Up Telephor of Tc 99m Tilmanocept:	ne Call 5 ± 3 Days Post-Injection		
	Concomitant medica	tion review		
	Assessment of adverse events			
Planned study dates	Planned study dates Start of study recruitment / November 2018			
	End of Study/September 2018			
Planned number of study centers	Approximately 1-3 centers in the United States			
Number of subjects	Up to 12 evaluable subjects may be enrolled.			
.	J,			

Confidential Page 11 of 71

Primary Endpoint	Proportion of subjects experiencing a noxious pharmacologic activity/adverse drug reaction (ADR)	
Secondary Endpoints	Determine the three dimensional tessellation localization of Tc 99m tilmanocept by planar and SPECT/CT imaging in subjects with NASH and asymptomatic controls.	
	Determine the three dimensional tessellation localization of unfiltered Tc 99m sulfur colloid by planar and SPECT/CT imaging in subjects with NASH and asymptomatic controls.	
	Comparison of liver localization distribution tessellation pattern intensities between Tc 99m tilmanocept and unfiltered Tc 99m sulfur colloid	
Exploratory Endoints	*	

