9.5.3 Analysis of Efficacy Variables

Co-location of tilmanocept and sulfur colloid intrahepatic tessellation localization (Figure 7) will be assessed through frequency tables derived by creating virtual slices of the liver.. These scans will be false-colored and overlaid, matching landmarks (e.g. large blood vessels) for image registration. The resulting voxel colors will be classified as binding tilamanocept, binding sulfur colloid, or binding both. No formal hypothesis tests are planned. Frequency tables will created for individual subjects and overall.

The voxel radiation intensities will be used to create non-parametric density estimates of ^{99m}Tc gamma radiation intensities for both Tc 99m tilmanocept and Tc 99m sulfur colloid. Density estimates will be created for both individual subjects and for NASH subjects and healthy controls pooled separately.

[figure not shown]

Figure 7. Diagrmatic representation of anticipated tessellation

Complete analyses and details will be described in the Statistical Analysis Plan (SAP) for the study.

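### Site-specific image settings plus voxel pooling with no stated subject weight can let scanner settings, and to a lesser degree liver size, drive the overall table and the NASH and control densities

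*Combined protocol and SAP*

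**What the plan says.** **Acquisition (Section 8.2).** Some settings are common to all sites: a dual-headed camera, a low-energy high-resolution collimator, an energy window around 140 keV and a planar count target. The rest is local. SPECT slices are reconstructed with the manufacturer's "recommended reconstruction algorithms including the recommended attenuation correction", and the section strongly recommends that "each site should perform all imaging acquisitions per their camera manufacturer and model parameters and in accordance with their institutional practices". It states no matrix, voxel size, filter or iteration count. The Synopsis plans for "Approximately 1-3 centers in the United States".

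**Analysis (Section 9.5.3).** For each subject the sulfur colloid and tilmanocept images are combined: "These scans will be false-colored and overlaid, matching landmarks". Each voxel is then classed as binding tilmanocept, sulfur colloid or both. Frequency tables are made for each subject and overall. Voxel intensities also feed non-parametric densities: "Density estimates will be created for both individual subjects and for NASH subjects and healthy controls pooled separately". The section mentions no common grid, resampling, intensity scale, liver-volume adjustment or weight per subject. No hypothesis tests are planned. Full details are deferred to an SAP whose text is not in the combined document.

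**The concern.** The unit that is counted is the voxel, and the number of voxels a liver contributes depends on the scanner grid as well as on the liver. If voxels from several subjects go into one table or one density, a subject scanned on a finer grid counts for more. That has nothing to do with NASH or with either agent.

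The groups are small. Section 8.1.1 allows up to six NASH subjects and six controls, and Section 5.2 plans a review comparing three with three. In groups of that size, an uneven weight can turn a group summary into a description of one or two people. The three secondary objectives all concern imaging, so the pooled imaging summaries are what a reader would take away on localization.

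**Working it through.** The plan gives no figure for voxel size, liver volume or subject weight, so there is none to reproduce. Its N=12 is stated without a formula and is not affected here.

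**Formulas**
- Voxels from a subject = liver volume / (voxel side)³.
- Weight of a subject when voxels are pooled = own voxels / all pooled voxels.
- Effective number of subjects (Kish) = (sum of weights)² / (sum of squared weights).

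**Inputs**
- From Section 8.2: a nominal field of view 20 inches on the long side, which is 20 × 25.4 = 508 mm.
- Assumed, because the documents give none: cubic voxels, matrices of 64 or 128 across that field, a milder pair of 4.0 and 4.8 mm voxels, and liver volumes of 1.2 to 2.5 L.

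**Voxel size**
- 508/64 = 7.94 mm and 508/128 = 3.97 mm.
- A 1.5 L liver then holds about 3,000 or about 24,000 voxels. The ratio is (128/64)³ = 8.
- For the milder pair the ratio is (4.8/4.0)³ = 1.73.

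**Weights in a pooled group**

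| Scenario (equal livers unless stated) | Weight per subject | Effective n |
|---|---|---|
| Three subjects, one at 128 and two at 64 | 8/10 = 80%, 10%, 10% | 10²/66 = 1.52 of 3 |
| Six subjects, three at 128 and three at 64 | 8/27 = 29.6%, 1/27 = 3.7% | 27²/195 = 3.74 of 6 |
| Six subjects, three at 4.0 mm and three at 4.8 mm | 21.1%, 12.2% | 5.60 of 6 |
| Three subjects, same voxel, livers 1.2, 1.5 and 2.5 L | 23%, 29%, 48% | 5.2²/9.94 = 2.72 of 3 |
| Twelve overall, same voxel, NASH 2.0 L and controls 1.5 L | 9.5%, 7.1% | 11.76 of 12 |

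**Effect on a result.** Suppose three subjects have 60%, 30% and 30% of voxels in the class that binds both agents.
- Weights 8:1:1 give (8×60 + 30 + 30)/10 = 54%.
- Equal weights give (60 + 30 + 30)/3 = 40%.
- Liver size alone (2.5, 1.5 and 1.2 L, in that order) gives (150 + 45 + 36)/5.2 = 44%.

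**Intensity axis.** Section 9.5.3 names no unit. If intensity means counts per voxel, the same uptake per unit volume gives one eighth of the counts in a voxel with one eighth of the volume. The density would then shift along its axis as well as being unevenly weighted.

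**After the change.** With each subject summarized first and averaged equally, weights are 1/3, 1/6 or 1/12 and effective n is 3, 6 or 12. A common grid alone removes the voxel-size rows of the table but leaves the liver-size rows.

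**The case against.** **The pooling rule is inferred.** Section 9.5.3 does not say that raw voxels are concatenated without weights, and the deferred SAP could set a common grid and equal subject weights. This stands as a limit. Concatenation is the plain reading, but the firm statement is that the grid and weights are not given. An SAP could settle the weighting; requirements on acquisition belong in Section 8.2.

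**The large figures are chosen.** The 80% needs mixed 64 and 128 grids in a group of three, and a single center is allowed. The milder voxel pair leaves 5.60 of 6 effective subjects, and liver size alone leaves 2.72 of 3. This also stands: 80% is a possible case, not an expected one.

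**Much of the output is untouched.** Per-subject tables and densities do not depend on weights between subjects. The primary endpoint is safety, so no error rate or power changes. On a common grid, weighting by volume has a meaning of its own, the share of pooled liver tissue. All of this is right and limits the weight of the point.

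Three stronger readings are tempting, and the documents do not support them:
- *That sites choose the energy window.* Section 8.2 sets 15% and allows 20% only where a camera lacks the 15% setting. It also fixes the collimator type.
- *That SPECT-only imaging is allowed.* The camera "should be a dual-headed SPECT or SPECT/CT camera equipped with a low-energy, high-resolution collimator", which could be read that way. But Section 8.2 itself, Section 3.1 and the visit descriptions in Section 7.2 call for SPECT/CT at every imaging time point, and Section 3.2 explains that planar imaging on a SPECT camera is combined with SPECT/CT.
- *That the comparison of the two agents within a subject is already compromised.* Nothing says that settings change between Day 0 and Day 3. Following one site's usual practice points towards consistency, and registration may put both scans on one grid. The gap is only that a change is not ruled out.

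**Conclusion.** The point holds in conditional form. Section 8.2 recommends local settings and Section 9.5.3 pools voxel results without a stated grid, intensity normalization or subject weight. On the plain reading, a subject's weight in the overall frequency table and in the NASH and control densities is proportional to liver volume divided by voxel volume.

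If cameras or settings differ between subjects, scanner settings can drive those outputs. The weight ratio is 1.73-fold for 4.0 against 4.8 mm voxels and 8-fold for a 128 against a 64 grid, both assumed. With one site and one protocol, only the liver-size effect is left, and it is smaller in these examples.

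The affected outputs are exactly those named: the frequency table is planned per subject and overall, while the NASH and control pooling applies to the densities. It would go too far to infer that one subject will dominate, because the documents give no grid. The change is worth making because it is cheap and because these are the plan's group-level voxel summaries.

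**What to change.** **Section 8.2.** Require the same camera, acquisition settings and reconstruction for all of a subject's sulfur colloid and tilmanocept scans.

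**Section 9.5.3 (and the SAP).**
- Resample all studies to one stated voxel size.
- Compute each subject's class percentages and normalized density first, on a stated intensity scale.
- Form the overall table and the NASH and control densities as equal-weight averages over subjects. A volume-weighted version may be shown as a supplement.

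Both parts of the analysis change are needed, since a common grid alone leaves the liver-size weighting. Resampling equalizes the grid but does not remove differences in resolution or reconstruction between cameras, so the per-subject results should stay in view beside the averages.

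**Cost.** One site instruction, a few lines of analysis text and slightly more image processing. A site with several cameras must book the same one for both visits. The sample size and the primary endpoint do not change.

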8.3 Pharmacokinetics

No pharmacokinetic investigation will be performed in this study.

Clinical Study Protocol Number: NAV3-30

8.4 Safety

8.4.1 Adverse Events

8.4.1.1 Definition of Adverse Event

The definitions below follow International Conference on Harmonization (ICH) – Good Clinical Practice (GCP) (see also ICH Guideline for Clinical Safety Data Management: Definitions and Standards for Expedited Reporting).

Adverse Event (AE)

An AE is defined as any untoward medical occurrence in a subject administered a pharmaceutical product and which does not necessarily have a causal relationship with this treatment. An AE can therefore be any unfavorable and unintended sign (including an abnormal laboratory finding), symptom, or disease temporally associated with the use of a medicinal (investigational) product, whether or not considered related to the medicinal (investigational) product.

Any clinically significant change in a condition (worsening) from screening that results in a change in subject management will be considered an AE and will be recorded on the AE page of the CRF.

By definition for this study, all untoward medical occurrences beginning on the day of Visit 1 Screening (Days -45 to -1) through the assessment of the Safety Follow-up Telephone Call (Day 8 ± 3) are to be reported as AEs. AEs continuing after study completion will be followed to normalization or stabilization. SAEs will be reported from the time of consent through the end of participation.

